If the change represents more than minimal risk to subjects, it must be reviewed and approved by the IRB at a convened meeting. For a modification to be considered more than minimal risk, the proposed change would increase the risk of discomfort or decrease benefit. The IRB must review and approve the proposed change at a convened meeting before the change can be implemented unless the change is necessary to eliminate an immediate hazard to the research participants. In the case of a change implemented to eliminate an immediate hazard to participants, the IRB will review the change to determine that it is consistent with ensuring the participant's continued welfare. Examples: Convened Board Increase in target enrollment for investigator initiated research or potential Phase I research Expanding inclusion or removing exclusion criteria where the new population may be at increased risk Revised risk information with active participants Minor risk revisions that may affect a subject's willingness to continue to participate Expedited Review Increase in target enrollment at Penn where overall enrollment target is not exceeded or potentially sponsored research Expanding inclusion or removing exclusion where the new population has the same expected risk as the previous, based on similarities of condition Revised risk information with subjects in long-term follow-up Minor risk revisions with no subjects enrolled to date

Expedited Review

Modification Summary

Please describe any required modification to the protocol. If you are using this form to submit an exception or report a deviation, enter 'N/A' in the box below.

Increase in total enrollment in order to apply the study intervention in 20 subjects. To date, 4 subjects have enrolled (defined by provision of informed consent) who subsequently became ineligible and could not undergo the intervention. We will increase total enrollment to 30 subjects, in order to allow for these subjects who enroll but become ineligible after consent, but will consider accrual complete when 20 subjects undergo the study intervention.

Risk / Benefit

Does this amendment alter the Risk/Benefit profile of the study?

No

Change in Consent

Has there been a change in the consent documents?

No

If YES, please choose from the options below regarding re-consenting

Deviations

Are you reporting a deviation to this protocol?*

No

Exceptions

Are you reporting an exception to this protocol?*

No

Protocol Details

Resubmission*

Yes

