The objective of the proposed research is to evaluate a promising strategy for CPAP level selection: a physiologic approach minimizing V/Q mismatch and measured non-invasively at the infants bedside. We propose the following specific Aims and hypotheses in support of this objective: Aim 1 (primary): measure the responsiveness of V/Q mismatch to a strategy of individualized CPAP level selection. We hypothesize that V/Q mismatch will, on average, improve by 10% of baseline V/Q mismatch at the best identified CPAP level. Aim 2: describe the distribution of best CPAP levels as identified by our strategy. Best CPAP levels will be described as both absolute values and relative to baseline (+2 cm H₂O, -1 cm H₂O, etc.). For this exploratory aim, we hypothesize that a best CPAP will be identified above the baseline in greater than 50% but less than 80% of subjects. Demonstrating that most but not all infants benefit from higher pressures will highlight the importance of individualized CPAP level selection in premature infants.

Primary outcome variable(s)

Primary outcome measure: V/Q mismatch. This parameter will be calculated by computer software on the basis of the curvilinear characteristics generated by a best-fit curve connecting the FiO₂/SpO₂ pairs obtained during the study protocol. With lower V/Q and greater mismatch, the curve is progressively displaced to the right relative to a curve corresponding to an ideal reference lung (interrupted, left-most curve in Figure 2, see attached documents). The V/Q ratio is displayed on the software output after the FiO₂/SpO₂ pairs are input. Additionally, this parameter is also displayed as the degree of right-shift relative to the ideal reference lung (greater values indicate more mismatch), providing a positive continuous number with units of % FiO₂ as an alternative measure to the ratio value with greater ease of use. This will be measured twice at baseline without a change in CPAP level and then following each CPAP level change. The primary outcome measure is the responsiveness of V/Q mismatch to a strategy of individualized CPAP level selection, measured as the improvement in V/Q mismatch between the second baseline level and best identified CPAP level for each subject (see Figure 3 in attached documents.) For infants not responding to either +1 or -1 cm H₂O CPAP level changes, baseline CPAP will be defined as best, with zero assigned as the improvement in V/Q mismatch.

Secondary outcome variable(s)

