Secondary outcome: best CPAP level. Our second Aim is to describe the distribution of best CPAP levels as identified by our strategy. We hypothesize that best CPAP will vary between infants, resulting in a distribution of values. Best CPAP level will be identified as the lowest CPAP level associated with an improvement greater than 5% in V/Q mismatch relative to the preceding CPAP level, as described in the study protocol. This will be "measured" once at the conclusion of the study protocol. Excessive

airway pressures can result in lung over-distension and can plausibly result in adverse cardiopulmonary interactions through transmission of positive pressure to the heart and intra-thoracic vessels (however, this has not been observed in any modern CPAP level studies performed in premature infants, see Table 1). We will measure the impact of CPAP level changes on the following readily available clinical cardiovascular parameters during the study protocol: Mean arterial blood pressure will be measured with a neonatal blood pressure cuff used for routine clinical care and placed on an upper extremity or through pressure transduction of an indwelling arterial catheter, when present (uncommon in our subject population), with units of mm Hg. This outcome will be recorded at the end of each baseline and CPAP level period by the research team. Heart rate will be measured and displayed by the study pulse oximeter, with units of beat per minute. This outcome will be recorded at the end of each baseline and CPAP level period by the research team. Additional data to be collected will include: i) demographic data; (gestational age, birth weight, gender, race, etc.) ii) baseline variables (receipt of antenatal steroids, Apgar scores, age in hours and FiO₂ at intervention, most recent hemoglobin level, CPAP pressure source and interface, etc.) and iii) important or pertinent in-hospital neonatal outcomes (survival to discharge, BPD, brain injury by ultrasound, patent ductus arteriosus, necrotizing enterocolitis, retinopathy of prematurity, duration of: MV days, CPAP and supplemental oxygen, etc). This data will be used to explore associations between these variables and both a) baseline V/Q mismatch and b) the responsiveness of this parameter to CPAP level changes, with a goal of supporting hypothesis generation for subsequent research

Background

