
No active consideration of endotracheal intubation; as determined by the clinical Attending of record. 2. No hemodynamic instability, defined as a baseline heart rate less than 100 beats per minute (bpm) or greater than 180 bpm; or a mean arterial blood pressure of less than 30 millimeters of mercury (mm Hg). 3. No supplemental FiO₂ requirement greater than 0.45. 4. No capillary/arterial partial pressure of carbon dioxide greater than 65 mm Hg on last blood gas analysis, unless performed more than 6 hours prior. 5. No more than 6 apnea/bradycardia/desaturation events requiring tactile stimulation or more than 1 requiring positive pressure bag ventilation in the preceding 6 hours. Initiation of the study protocol will be deferred until these criteria are met. Figure 3 depicts the study protocol as applied in one hypothetical subject. Of note, the protocol will vary between subjects with respect to the direction and extent of CPAP level changes, as determined by the absence or presence of a response at each step-wise CPAP level change. This is described in detail below. Subjects will undergo the study interventions in their routine clinical environment. The clinically selected CPAP interface and pressure source will be maintained. A study pulse-oximeter, with low motion artifact and a short averaging time, will be placed on a post-ductal limb and used for SpO₂ measurements. V/Q will first be measured on two separate occasions 30 minutes apart at baseline CPAP, set by the clinical team. The repeat baseline measures will allow an estimate of the stability of V/Q as a function of time (further discussed in Confounding under Analysis Plan). To measure V/Q mismatch, gradual changes in delivered FiO₂, followed by SpO₂ measurement, will be applied to obtain three FiO₂/SpO₂ pairs, one each for SpO₂ values in the ranges of 85-87%, 89-91% and 93-95%. To obtain each SpO₂ range, FiO₂ will be titrated gradually until SpO₂ falls within the desired values. After 60 seconds of stabilization at the identified FiO₂ value, SpO₂ will be recorded every 30 seconds for 2 minutes if an adequate signal waveform is present, providing up to four SpO₂ values. These values will be averaged to calculate the SpO₂ value used for the FiO₂/SpO₂ pair, acknowledging the inherent instability of pulse-oximeter values over time in premature infants. A computer software program will immediately calculate V/Q from the identified FiO₂/SpO₂ pairs at the bedside. Next, CPAP will be increased by +1 cm H₂O. A period of 15 minutes will elapse to allow equilibration of lung volumes in response to the CPAP level change (24). V/Q calculations as described above will be repeated. A positive response will be defined as an improvement in V/Q at the new pressure level of 5% relative to the preceding CPAP level. Responders will undergo subsequent stepwise +1 cm H₂O increases up to +3 cm H₂O from baseline or 8 cm H₂O; whichever is less. Infants not responding to the initial +1 cm H₂O increase will return to baseline CPAP for 15 minutes and then be assessed at -1 cm H₂O from baseline. Infants responding at this lower CPAP level will undergo an additional decrease to -2 cm H₂O from baseline or 3 cm H₂O; whichever is greater. The allowed range of -2 to +3 cm H₂O reflects our institutional practice of typically setting a baseline CPAP level of 5 or 6 cm H₂O and a CPAP pressure range of 4 to 8 cm H₂O used in international trials. Best CPAP will be defined as the lowest (and last) CPAP level at which a positive response, as defined above, is measured. The baseline CPAP level will be defined as best for those infants not responding to either +1 or -1 cm H₂O CPAP level changes, with a corresponding V/Q improvement of zero. Upon completion of the study protocol, infants will be returned to their baseline CPAP level. The study protocol will typically require between 60 and 120 minutes. Throughout the study, a set of pre-defined stopping criteria will be monitored to ensure subject tolerance of the study procedures. These criteria are designed to be conservative safety measures and will result in study termination and provision of supportive care, as needed. Patient Safety Considerations: Extensive patient safety considerations minimizing the risks associated with implementation of this phase II design research protocol have been incorporated: 1. Many of the key eligibility (inclusions and exclusion) criteria reflect the deliberate selection of a premature infant population that is inherently less vulnerable and at lower risk of common morbidities of prematurity and less likely to suffer any adverse outcomes from implementation of the study procedures. a) I1. Corrected gestational age 27-35 weeks (GA): this selects a study population in which respiratory distress syndrome is common and CPAP is frequently used, while avoiding less mature infants with a CGA less than 27 weeks who are more prone to physiologic instability. We exclude this population in consideration of safety for this phase II study despite a high risk of CPAP failure and a potential for benefit from our long-term research goals of establishing methods to prevent CPAP failure. b) I2. Chronologic age of greater than 24 hours. This avoids study of infants during the first 24 hours of life when they may be more prone to physiologic instability. c) I3. On continuous CPAP support for greater than 24 hours. This prioritizes safety by restricting study to subjects demonstrating stability on CPAP therapy, in contrast to infants newly transitioned to CPAP without a period of demonstrated tolerance. d) I4. Supplemental oxygen requirement, with a fraction of inspired oxygen (FiO₂) 0.25 for at least 2 consecutive hours. This ensures that CPAP level changes are only performed in infants requiring supplemental oxygenation, suggesting V/Q mismatch and/or shunt from atelectasis. These subjects would plausibly benefit from carefully monitored changes in continuous distending airway pressure to counteract the pathophysiology resulting in the oxygen need. This criteria avoids CPAP

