
level changes in infants on CPAP but not requiring supplemental oxygen as they are less likely to benefit from changes in pressure level. e) E2. Exclusion of infants with current or prior air leak syndrome. This avoids study in infants with suggestion of a pathophysiology that could worsen with increased CPAP levels. 2. To further avoid study in infants with physiologic instability, the following criteria will be met prior to initiation of the study procedures; with deferral of the study until they are met: a. No active consideration of endotracheal intubation; as determined by the clinical Attending of record. b. No hemodynamic instability, defined as a baseline heart rate less than 100 beats per minute (bpm) or greater than 180 bpm; or a mean arterial blood pressure of less than 30 millimeters of mercury (mm Hg). c. No supplemental FiO₂ requirement greater than 0.45. d. No capillary/arterial partial pressure of carbon dioxide greater than 65 mm Hg on last blood gas analysis, unless performed more than 6 hours prior. e. No more than 6 apnea/bradycardia/desaturation events requiring tactile stimulation or more than 1 requiring positive pressure bag ventilation in the preceding 6 hours. 3. Stepwise changes in CPAP level, with assessment after each CPAP level change and restriction of further pressure changes to instances in which there is a response suggestive of improving physiology - defined as greater than a 5% improvement of baseline V/Q mismatch. Infants who are at inadequate lung volumes at baseline CPAP are likely to show benefit with higher pressure levels, while infants with adequate lung volumes at baseline CPAP are unlikely to show any physiologic benefit at higher pressure levels. Similarly, infants with over distended lung volumes at baseline may benefit from lower pressure levels, while infants with adequate lung volumes at baseline CPAP are unlikely to show benefit with lower pressure levels. This key element of study procedures will protect against the risk of over-distension or loss of lung volumes secondary to the study procedures. 4. Stopping Criteria. The following "stopping criteria" will be monitored in each subject throughout the study procedures and will result in study termination, provision of supportive care and a return to baseline settings when appropriate: a) a drop in mean arterial pressure to a mmHg value less than 30 mm Hg and in excess of 10% from the baseline value, or in excess of 20% of baseline value. b) an increase in heart rate to greater than 190 bpm and in excess of 10% from the baseline value or in excess of 20% of the baseline value. c) with an adequate pulse waveform, a sustained drop in SpO₂ to less than 80% for greater than one minute or a drop in SpO₂, to less than 75% for greater than 30 seconds or less than 45% for any duration of time. d) a two-fold increase in the hourly frequency of cardiorespiratory events (apnea/ bradycardia/desaturation) relative to the average frequency in the four hours prior to study initiation. For infant without any events in the four hours prior to study initiation, greater than one event per hour will be used as a threshold. Further, any single event requiring bag- mask positive pressure ventilation will lead to study termination.

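### The heart-rate and MAP test covers only the selected, tolerated CPAP level, and early terminations are one pooled proportion judged against consented rather than treated infants.

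*Combined protocol and SAP*

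**What the plan says.** - **Objectives, Secondary outcome variable(s).** The stated intention is: "We will measure the impact of CPAP level changes on the following readily available clinical cardiovascular parameters during the study protocol". The timing given for MAP, and again for heart rate, is: "This outcome will be recorded at the end of each baseline and CPAP level period by the research team".
- **Analysis Plan.** Heart rate and blood pressure are compared between baseline and best CPAP only, by the Aim 1 method (paired t-test or signed-rank test). The prediction is no significant difference.
- **Study Procedures, Procedures.** V/Q at a new level is measured after a 15-minute wait and the oxygen titrations. "Best CPAP will be defined as the lowest (and last) CPAP level at which a positive response, as defined above, is measured". For the rest: "The baseline CPAP level will be defined as best for those infants not responding to either +1 or -1" cm H₂O.
- **Procedures, Stopping Criteria.** Four groups of criteria, (a) MAP, (b) heart rate, (c) SpO₂ and (d) cardiorespiratory events, are watched throughout and end the session. Criterion b reads "an increase in heart rate to greater than 190 bpm and in excess of 10% from the baseline value", or a rise of more than 20% of baseline.
- **Data and Safety Monitoring.** The proportion of infants stopped early under these rules will be documented and is expected to be below 20% of those enrolled. A committee reviews safety data after 7 and 14 enrolled.
- **Modification Summary and Accrual.** Enrolment means consent: "4 subjects have enrolled (defined by provision of informed consent) who subsequently became ineligible and could not undergo the intervention". Up to 30 may be enrolled so that 20 are evaluated.

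**The concern.** The outcome section asks what CPAP level changes do to the circulation. The test asks what happens at one level per infant, picked because gas exchange improved there. Two kinds of reading are left out:

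1. Period-end readings at levels that gave no V/Q response. They are collected but not compared. This happens even if no session is ever stopped.
2. Reactions large enough to stop a session before V/Q is measured at that level. That level cannot be best CPAP, and no scheduled period-end reading exists for it.

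The second kind is left out because the reaction was large. The termination proportion is where such infants would be seen. As planned it does not separate cardiovascular stops from desaturation or apnea stops, and its benchmark counts infants who were never exposed. A reader given a non-significant heart-rate change and a single termination percentage could not tell whether any stop was for heart rate or MAP. The Study Design section names safety monitoring as a goal of the trial, so this affects what can be concluded.

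**Working it through.** **Plan's own figure.** The only computed figure is for Aim 1: mean change 10%, SD 15%, n = 20, two-sided 0.05. The noncentral t gives 80.7% power, and 20 is the smallest n reaching 80%. It reproduces and is not at issue. The heart-rate/MAP test has no stated power basis.

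**Which infants the plan already settles.**

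| Course of session | Best CPAP | Reading in the test |
|---|---|---|
| No response at +1 or -1 | Baseline | Readings at +1 and -1 stay out |
| Response at +1, stopped at +2 before V/Q is measured | +1, as last responding level | +1 reading enters; reaction at +2 stays out |
| Stopped at +1 before V/Q is measured | Not stated | Not stated; reaction stays out |

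Only the last type of row, a stop before any response, is open.

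**How large a reaction must be to stop a session.** Infants do not start with "a baseline heart rate less than 100 beats per minute (bpm) or greater than 180 bpm", so baseline B lies between 100 and 180 bpm. Criterion b fires when the rise exceeds min(0.20B, max(190 − B, 0.10B)).
- Smallest limit: 190 − B = 0.10B gives B = 172.7 and a limit of 17.3 bpm.
- Largest limit: 190 − B = 0.20B gives B = 158.3 and a limit of 31.7 bpm.

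Criterion a, for baseline MAP M of at least 30, fires when the fall exceeds min(0.20M, max(M − 30, 0.10M)). That is 3 mm Hg at M = 30 and 8 mm Hg at M = 40.

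Each omitted criterion b stop is therefore a rise of more than 17 bpm at that moment. It may be brief, since the criterion has no minimum duration.

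**Termination proportion by denominator.** Twenty infants start the procedures, and 24 or 30 have been enrolled by then (30 is the cap; 24 is an assumed alternative).

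| Stops | of 20 started | of 24 enrolled | of 30 enrolled |
|---|---|---|---|
| 3 | 15.0% | 12.5% | 10.0% |
| 4 | 20.0% | 16.7% | 13.3% |
| 5 | 25.0% | 20.8% | 16.7% |

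With 30 enrolled, four or five stops meet the below-20% expectation. Among infants started, neither does.

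**Effect on the heart-rate test: illustration with assumed inputs.** Simulated t-test in 20 infants. The change is normal in V/Q responders and zero otherwise. 65% respond, which is the middle of the plan's hypothesis that "best CPAP will be identified above the baseline in greater than 50% but less than 80% of subjects". Every crossing of the limit is taken to be mid-period.

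| Mean / SD of change; baseline | Crossings among responders | Power, all readings | Power, stopped infants handled as shown |
|---|---|---|---|
| 10 / 15; 165 bpm | 15.9% | 58% | 32% if dropped |
| same | 15.9% | 58% | 54% if entered at an earlier level with half the rise |
| 10 / 15; 155 bpm | 8.1% | 58% | 45% if dropped |
| 5 / 10; 165 bpm | 2.3% | 37% | 34% if dropped |
| 3 / 8; 165 bpm | 0.3% | 23% | 23% if dropped |

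The first row implies 20 × 0.65 × 0.159 = about 2 heart-rate stops. If the infants who cross would not have responded on V/Q, stopping costs nothing (31.5% against 31.7%).

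**The case against.** The strongest reply is that this is an ancillary, unpowered comparison with several safeguards around it, and much of that reply stands.

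- A reader might infer that the plan has no rule for stopped infants. It does for most: one who responded at an earlier level keeps that level as best, and its heart rate and MAP were already recorded. Only a stop before any response is open.
- A reader might infer that the test loses nearly half its power (58% to 32%). The documents do not support that. Every input is assumed, all stopped infants are dropped, and all crossings are mid-period. Entering an earlier tolerated level gives 54%, and smaller reactions cost 3 points or almost nothing.
- A reader might blame stopping for all of the selection. Restricting the test to best CPAP selects on V/Q response even with no stops.
- A reader might give MAP equal weight. Cuff MAP is scheduled at period end and arterial catheters are described as uncommon, so mid-period stops are mainly a heart-rate matter.
- A reader might infer that reasons for stopping will be withheld. The plan is only silent. The committee reviews and the planned descriptive statistics leave room for a breakdown.
- The 20% figure is an expectation with no action attached, so its denominator changes no decision rule.

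The reply does not remove the mismatch between the promised outcome and the test, the absence of any planned listing by criterion, or the use of consented infants as the benchmark.

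**Conclusion.** The point holds in limited form, as something to consider. Followed as written, the plan yields a heart-rate/MAP comparison confined to levels selected for V/Q response and tolerated, and a termination benchmark diluted by infants who never had the procedures.

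The dilution is simple arithmetic: five stops are 16.7% of 30 enrolled and 25% of 20 treated, if enrolment reaches its cap. The effect on the heart-rate/MAP test cannot be sized from the documents. Its stopping part is nil unless a criterion a or b stop occurs before V/Q is measured at that level. The selection on V/Q response is present regardless. Aim 1, its sample size and the stopping limits are unaffected.

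**What to change.** 1. **Objectives, Secondary outcome variable(s):** at each stop, record the criterion that fired, the CPAP level, the heart rate, and MAP if already available. No extra cuff inflation is needed.
2. **Data and Safety Monitoring:** use infants who started the procedures as the denominator, both for the documented proportion and for the 20% expectation. Report terminations by criterion (a to d) and CPAP level beside the heart-rate/MAP results.
3. **Analysis Plan:** keep the planned test. Add a descriptive summary of the period-end heart rate and MAP already collected at every level tested. Say what an infant stopped before any response contributes. Limit the conclusion to the selected, tolerated level, read together with the criterion a and b stops.

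The cost is a short entry at each stop, a small table and a few sentences. The safety statement may look less favourable. Infants have already been enrolled, so earlier stops may lack recorded values; these can be listed by criterion where known and otherwise as not recorded.

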This study will enroll up to 30 patients in order to evaluate 20 subjects. Infants will be screened for eligibility by the research team using routinely available clinical data from the electronic health record. Informed consent will be obtained from parents or guardians approached within the HUP ICN, PAH ICN, or the CHOP N/IICU during the eligibility window as described below. The diagram depicted in Figure 4 summarizes expected enrollment in consideration of our eligibility criteria and additional barriers to successful recruitment and study application. This estimate suggests a 10-month window of active enrollment will be required to meet our recruitment goals, making our one-year recruitment goal feasible. Aim 1 guides sample size considerations. Using a paired test of correlated means, a sample size of 20 evaluated infants will provide 80% power to detect an overall average percent change of 10% from baseline, assuming a 15% standard deviation of the difference and a two-sided alpha level of 0.05.

Key inclusion criteria

I1. 27-35 weeks corrected gestational age (CGA) by best obstetric estimate, determined by the clinical obstetric team during antepartum admission and chronologic age, measured from date of birth I2. Chronologic age greater than 24 hours, measured from time of birth. I3. On CPAP support between 4-8 cm H₂O for greater than 24 hours, as document on the bedside infant flow sheet. I4. Supplemental oxygen requirement, with a fraction of inspired oxygen (FiO₂) 0.25 for at least 2 consecutive hours, as documented on the bedside infant flow sheet. (Infants without an oxygenation requirement are unlikely to have significant V/Q mismatch. Further, FiO₂ titrations (see Procedures) are required to apply the non-invasive technique, resulting in limited applicability to infants with little or no supplemental oxygen requirement).

Key exclusion criteria

E1. Congenital anomalies, as determined by the clinical supervising physician. E2. Current or prior air leak syndrome, as determined by the clinical supervising physician.

Vulnerable Populations

Children Form

Pregnant women (if the study procedures may affect the condition of the pregnant woman or fetus) Form

Fetuses and/or Neonates Form

Prisoners Form

Other

None of the above populations are included in the research study

The following documents are currently attached to this item:

There are no documents attached for this item.

Populations vulnerable to undue influence or coercion

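### The stated 80% power is correct for a signed paired difference, but the primary outcome is zero or a gain of about 5% or more, so the figure does not describe the planned test

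*Combined protocol and SAP*

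**What the plan says.** The Accrual section (Characteristics of the Study Population) says that "a sample size of 20 evaluated infants will provide 80% power to detect an overall average percent change of 10% from baseline". The calculation is for a paired comparison of means, and its remaining inputs are given as "assuming a 15% standard deviation of the difference and a two-sided alpha level of 0.05". It does not mention the response rule.

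The outcome is defined elsewhere. Primary outcome variable(s) takes the improvement from the second baseline measurement to the best CPAP level. For infants who respond to neither first step, "baseline CPAP will be defined as best, with zero assigned as the improvement in V/Q mismatch". Procedures sets a positive response at a 5% improvement on the preceding level and adds: "Best CPAP will be defined as the lowest (and last) CPAP level at which a positive response, as defined above, is measured".

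The Analysis Plan tests this outcome against no change, by paired t-test or, if the results are non-parametric, by Wilcoxon signed-rank test.

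The only indirect information on how many infants respond is the Aim 2 hypothesis that "a best CPAP will be identified above the baseline in greater than 50% but less than 80% of subjects". That counts upward responders only.

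**The concern.** A signed normal difference with mean 10% and SD 15% puts about a quarter of infants below zero and over a third below a 5% improvement. Under the response rule no infant can record a worsening or a gain well short of 5%; such an infant is scored zero. The power was therefore worked out for one quantity, and another will be tested.

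The power sentence is the only justification given for 20 evaluated infants, and the Modification Summary closes accrual at that number. A reader who takes it at face value would treat 10% as the effect this trial has a four-in-five chance of detecting. That reader might then take a significant result as support for the hypothesised 10%, and a non-significant one as a one-in-five miss. Neither reading is sound for an outcome that cannot go below zero.

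**Working it through.** **Inputs.** From Accrual: n = 20, mean 10%, SD 15%, two-sided alpha 0.05. From Primary outcome variable(s) and Procedures: zero for non-responders and a 5% response threshold. The responder share and the spread of gains are not in the documents; both are assumed and varied below.

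**1. The plan's own figure.** Noncentrality = (10/15) × √20 = 2.98, with 19 degrees of freedom and critical t = 2.093. Power = 80.7%. With n = 19 it is 78.5%, so 20 is the smallest size that reaches 80%.

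**2. What that model implies.** For a normal difference with mean 10 and SD 15, P(below 0) = Φ(−10/15) = 25% and P(below 5) = Φ(−5/15) = 37%.

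**3. What the outcome allows.** Best CPAP must be a level with a measured response, and each accepted step improves by about 5% or more on the one before. Whether the lowest or the last responding level is taken, the gain from the second baseline is about 5% or more. Otherwise the score is zero. This takes the first step, up or down, as judged against the second baseline.

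**4. Power for that outcome at the plan's mean and SD.** Let p be the responder share. For overall mean 10 and SD 15:

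- responder mean = 10/p
- responder variance = (10² + 15²)/p − (10/p)² = 325/p − 100/p²

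The variance is positive only if p > 100/325 = 0.31, so 31% is the smallest share compatible with these moments. Responder gains are assumed to be 5% plus a gamma excess with these moments.

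For the Wilcoxon test, zeros are dropped and all remaining values are positive, so with k responders the exact two-sided p-value is 2/2^k. This is 0.0625 at k = 5 and 0.031 at k = 6. Power is therefore P(k ≥ 6) for a binomial(20, p), whatever the size of the gains.

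| Responder share | Responder mean, SD | t-test power (simulated) | Exact Wilcoxon power |
|---|---|---|---|
| 31% | 32.3, 2.8 | 91% | 62% |
| 35% | 28.6, 10.6 | 91% | 75% |
| 40% | 25.0, 13.7 | 94% | 87% |
| 50% | 20.0, 15.8 | 97% | 98% |
| 60% | 16.7, 16.2 | 98% | over 99% |
| 80% | 12.5, 15.8 | 98% | over 99% |

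A lognormal excess in place of the gamma moves the t-test figures by less than one percentage point.

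**5. Alternative reading of the inputs.** If 10% and 15% describe the signed change before the rule is applied, the recorded outcome has mean about 12 and SD about 12, and power is over 99.9% with either test.

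**6. Rejection with no CPAP effect.** The Procedures steps were simulated with measurement noise only. The noise level is an assumption.

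| SD of a repeat difference | t-test rejects | Wilcoxon rejects |
|---|---|---|
| 2.8% | 3% | 0.1% |
| 4.2% | 51% | 17% |
| 7.1% | 93% | 79% |
| 15% | 99.7% | 99% |

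A high power figure for this outcome therefore says little by itself.

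**The case against.** The strongest reply is that the printed calculation is correct and conventional, and that the complaint concerns a distributional assumption. This stands: there is no arithmetic error in the Accrual section. With half or more of infants responding, power is higher than stated, so the mismatch does not show that 20 infants are too few.

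It is also fair that the documents do not fix a replacement figure. A reader might infer that true power is about 97% at the plan's own mean and SD. That needs three further assumptions: a responder share of about one half or more, a shape for the gains, and the t-test. The Aim 2 range is an exploratory hypothesis about best levels above baseline, not a total response rate. At lower shares the planned Wilcoxon alternative falls below 80%.

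A reader might further infer that the trial really has 80% power at a mean of only 3-4%. The documents do not support this. Such a figure arises if 30-40% of infants respond with a mean gain of 10%. That share lies outside the Aim 2 range, and the outcome SD is then about 5.5%, not 15%.

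Finally, the response rule leaves some cases open. Procedures does not say which baseline reading serves for the first step, and infants who meet the stopping criteria have no assigned outcome. So zero or about 5% or more describes the outcome as written, subject to those gaps.

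What remains is that the Accrual calculation does not model the response rule, and that the distribution it assumes is one the outcome cannot have.

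**Conclusion.** The concern holds as a mismatch between the sizing and the outcome. The printed 80% (80.7%) belongs to an unselected, signed difference and does not describe the test in the Analysis Plan. At outcome mean 10% and SD 15%, t-test power is 91-98% and exact Wilcoxon power runs from 62% to over 99%, depending on the responder share. Within 50-80% responding, both tests have 97% or more. These figures rest on the assumed responder share, on the 5%-plus-gamma gain for the t-test, on the first step being judged against the second baseline, and on every infant having a value.

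It would be tempting to replace power by a precision statement: 2.093 × 15/√20 gives a half-width of 7.0 points. That should not be printed as a 95% interval. Under the same assumed model, t-interval coverage is about 84-91% at 50-80% responding, and the interval carries the same selection of gains. Nor do the documents give grounds for setting aside the planned test and reading Aim 1 from such an interval alone.

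**What to change.** In the Accrual section:

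- State that the 80% applies to a signed paired difference with mean 10% and SD 15%.
- Replace or accompany it with power for the outcome defined under Primary outcome variable(s), over a stated range of responder shares and for both planned tests, with the assumed gain distribution printed.
- Beside the power, give the simulated rejection rate when CPAP level has no effect, with the assumed measurement noise, so that a high figure is not read as reassurance.
- Add that p<0.05 on this non-negative outcome is not evidence of a 10% improvement.

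Leave the 20 evaluated infants unchanged. The cost is a reworded paragraph and one short simulation, with no extra infants or procedures. The sponsor gives up the simple statement of 80% power for a 10% change.
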